### 2.2.3 Endpoint WP3

We will define the functional and structural neural substrates of critical cognitive functions in preterm children, determine the extent to which behavioural atypicalities are domain-specific versus domain-general, and, using perinatal data, characterize factors that explain the neural bases of cognitive impairment and resilience at 5-years (WP3).

### 2.2.4 Endpoint WP4

We will engage and involve parents and advocacy to guide the design, delivery and dissemination of the programme and to plan follow-on work that arises from it (WP4).

## 3 STUDY DESIGN

**WP1 is a national population-based cohort study:** >100,000 infants born in the UK with gestational age (GA) <32 weeks between 01/01/2008 & 31/12/2019 (National Neonatal Research Database, NNRD). Records will be linked between three databases: NNRD, National Pupil Database and the ScotXed Pupil Census.

**WP2 is an exposure-based short-term cohort study:** 300 mother-infant dyads (200 preterm with GA <32 weeks [exposed], 100 term with GA >37 weeks [non-exposed comparators]), recruited from the Edinburgh Royal Infirmary. The preterm group will be identified from infants born to women who present with threatened preterm birth and for whom delivery is planned or expected at less than 32 weeks GA. Term controls will be identified from the labour ward or antenatal clinic.

**WP3 is an exposure-based longitudinal cohort study:** 300 children (200 preterm, 100 term) are participants in a long-term cohort study of the effect of preterm birth on brain growth.

**WP4 is a participatory project:** it will engage and involve a parent advisory group (n=6-8) and the Adult Preemie Advocacy Network.

## 4 STUDY POPULATION

### 4.1 NUMBER OF PARTICIPANTS

**WP1:** >100,000 infants born in the UK with gestational age (GA) <32 weeks between 01/01/2008 & 31/12/2019 (National Neonatal Research Database, NNRD).

**WP2:** 300 mother-infant dyads: 200 preterm deliveries with GA <32 weeks (exposed, cases); 100 term deliveries with GA >37 weeks (non-exposed, comparators).

**WP3:** 300 children (200 preterm, 100 comparators).

## 4.2 INCLUSION CRITERIA

**WP1:** All neonates with GA < 32 weeks born in Great Britain and admitted to a neonatal unit. Data are available from England and Wales from 2012, and from Scotland from 2014.

**WP2:** Exposed: 300 preterm infants born at <32 weeks of gestational age (GA). Non-exposed comparators: 100 term infants born at >37 weeks of GA\*.

Preterm infants are included if a mother booked her pregnancy and delivered at Simpson Centre for Reproductive Health (SCRH, the study centre), or if a mother booked her pregnancy at a hospital outside the study centre but was transferred to it with her baby *in utero* due to planned or expected birth <32 weeks. Preterm infants who are transferred to SCRH *ex utero* for intensive care are not included.

\*GA is estimated based on first trimester ultrasound.

**WP3:** 300 participants (200 preterm infants and 100 comparators) in Theirworld Edinburgh Birth Cohort will be invited for MRI and cognitive assessments at age 5 years.

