# 9 STATISTICS AND DATA ANALYSIS

## 9.1 SAMPLE SIZE CALCULATION

**WP1.** The NNRD contains data from >100,000 infants in the required gestational range and 2-year outcome data are available for >60% (>70% in most recent years). Data completeness is high for key perinatal variables e.g., 90% for postcode at time of birth (used to derive deprivation index) and 93% for maternal age, and is lower for others e.g., maternal ethnicity 78%. We will investigate whether there are systematic patterns in missingness and we will analyse whether data imputation improves prediction models (univariate imputations using the mean/median values, and joint variable information-theoretic probabilistic methods for joint [conditional] distributions of variables).

Sensitivity analyses will be used to assess the impact of missing outcome data. In addition to applying statistical hypothesis testing (to assess p-values and statistical significance), we will also explore different statistical machine learning methods, including robust training and model validation using standard approaches (e.g. K-fold cross validation).

**WP2.** Sample size for groupwise comparisons of image data using biological variables is based on properties of the chosen EoP image phenotypes, and term and preterm differences we have observed in predictor variables (i) hair cortisol concentrations: 401pg/mg(262-615) versus 82pg/mg(55-169), respectively; and (ii) group differences in DNAm CRP scores.

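### WP2 has two preterm recruitment targets: 300 in section 4.2, 200 in sections 3 and 4.1; section 9.1 does not settle which governs.

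*Protocol*

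**What the plan says.** The protocol gives the WP2 group sizes in three places.

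- Section 3 (Study design): "300 mother-infant dyads (200 preterm with GA <32 weeks [exposed], 100 term with GA >37 weeks [non-exposed comparators"]).
- Section 4.1 (Number of participants): "300 mother-infant dyads: 200 preterm deliveries with GA <32 weeks (exposed, cases); 100 term deliveries with GA >37 weeks (non-exposed, comparators").
- Section 4.2 (Inclusion criteria): "Exposed: 300 preterm infants born at <32 weeks of gestational age (GA"), followed by "Non-exposed comparators: 100 term infants born at >37 weeks of GA".

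Section 9.1 says of WP2: "Sample size for groupwise comparisons of image data using biological variables is based on properties of the chosen EoP image phenotypes". It then adds term-preterm differences in two predictors. The first is hair cortisol, for which it gives "401pg/mg(262-615) versus 82pg/mg(55-169), respectively" (term first, preterm second). The second is DNAm CRP scores, for which it gives no figure. The image phenotypes are supported by citation only. No WP2 sample size, alpha, power, detectable effect or attrition appears in the section. For WP3, the same section gives an n, a power and a detectable correlation.

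**The concern.** A recruitment target is a figure that the study runs on. It decides when recruitment stops, how many families are approached, and how many sets of samples and 90-minute neonatal scans are planned. Two current passages say 200 preterm infants and one says 300, so as written the protocol cannot be followed in all three places.

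The natural next step is to look in section 9.1 for the number that was derived. That section gives no number, and the one quantified basis it offers is such a large difference that it cannot separate 200 from 300. A reader therefore cannot tell from the protocol's own calculation which target was intended.

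**Working it through.** **1. The counts.**

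| Section | Preterm | Term | Total | Ratio |
|---|---|---|---|---|
| 3 | 200 | 100 | 300 (stated) | 2:1 |
| 4.1 | 200 | 100 | 300 (stated) | 2:1 |
| 4.2 | 300 | 100 | 400 (by addition) | 3:1 |

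Sections 3 and 4.1 agree with each other and with their own stated total. Section 4.2 differs by 300 − 200 = 100 preterm infants, and 100/200 = 50%. Section 4.2 lists WP3 separately as 200 preterm and 100 comparators, so the 300 is not simply the WP3 preterm figure in the wrong place.

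**2. Can section 9.1 reproduce either number?** There is no WP2 figure in 9.1 to reproduce, so the check is what the cortisol contrast would require.

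Inputs from 9.1: term 401 (262-615), preterm 82 (55-169) pg/mg. Assumptions, none of which the protocol states for WP2: the brackets are interquartile ranges, the log scale is suitable, two-sided alpha is .05 and power is 90% (WP3 uses .05 and 90%).

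- Log difference: ln(401/82) = 1.587.
- Log SD = ln(Q3/Q1)/1.349. Term: ln(615/262)/1.349 = .633. Preterm: ln(169/55)/1.349 = .832.
- Pooled SD: √((.633² + .832²)/2) = .739.
- Standardised difference: d = 1.587/.739 = 2.15.
- Normal approximation: n per group = 2(1.960 + 1.282)²/d² = 4.6, so 5.
- Noncentral t, the better method at this size: power is .84 with 5 per group and .92 with 6. So 6 per group.

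Variants (normal approximation):

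| Variant | Total at 2:1 | Total at 3:1 |
|---|---|---|
| Pooled log SD, alpha .05, 90% power | 12 | 16 |
| Larger log SD (.832), alpha .05, 90% power | 15 | 16 |
| Larger log SD, alpha 5×10⁻⁸, 99% power | 75 | 92 |

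Reading the brackets as a 95% range instead gives totals of at most 12, even at the strictest alpha and highest power. On the raw scale with the larger SD, alpha .05 and 90% power, the requirement is 11 + 22 = 33 at 2:1. None of these gives 300 or 400. Power for the contrast is about 100% under both 200:100 and 300:100.

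**3. What the choice of number changes.** Same alpha and power as above.

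- Smallest detectable term-preterm difference in SD units = 3.2415 × √(1/100 + 1/n). For n = 200: 3.2415 × .1225 = 0.40. For n = 300: 3.2415 × .1155 = 0.37.
- Smallest detectable correlation within the preterm group = tanh(3.2415/√(n − 3)). For n = 200: tanh(.2310) = .227. For n = 300: tanh(.1881) = .186.

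The group comparison barely moves, because the 100 term infants limit it. Any analysis confined to preterm infants moves more.

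**The case against.** The best defence is that this is a one-figure slip in an eligibility section. Section 4.1 is the section headed for participant numbers, it agrees with section 3, and both match the 300-dyad total. The 300 in section 4.2 may be that total put in the wrong place. This is probably right and makes the repair easy, but the protocol does not say so, and the inclusion criteria still contradict the design.

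A second defence concerns section 9.1. Cortisol is one of three named bases, the image phenotypes come first, and they rest on cited work that is not reproduced in the protocol. Showing that cortisol needs few infants does not show that the WP2 number lacks a basis. That stands. All that follows is that the figures printed in 9.1 cannot identify the intended number.

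Three stronger readings are tempting and are not supported.

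- *WP2 is underpowered.* Both sizes far exceed what the cortisol contrast needs, and the protocol gives no image or DNAm effect against which to judge the rest.
- *Section 9.1 wrongly claims to have sized the mediation analysis.* It limits itself to groupwise comparisons of image data and makes no such claim. Hypothesis 2ii also asks whether the DNAm proxies are present in preterm infants, and a group contrast is relevant to that.
- *The choice of 200 or 300 decides whether the mediation test is adequate.* With both paths set at .20 in a preterm-only sample, a joint test has about 66% power at 200 and 88% at 300. But at n = 200, paths of .15 give about 32% and paths of .25 about 90%. The path sizes are assumptions, and sections 1.2 and 9.2 do not confine the mediation model to preterm infants.

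**Conclusion.** The contradiction holds and must be corrected: 300 preterm infants (400 in total, 3:1) in section 4.2 against 200 (300 in total, 2:1) in sections 3 and 4.1. It is read directly from current text and rests on no assumption.

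The finding on section 9.1 is narrower. It states no WP2 number, and its only quantified basis needs about 6 infants per group, so neither target follows from it. The figure of 6 depends on reading the brackets as interquartile ranges and on conventional alpha and power, but every variant checked stays far below both targets.

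For precision, the difference between the targets is small for term-preterm comparisons (0.40 against 0.37 SD) and larger for preterm-only correlations (about .23 against .19). These values assume complete data; no allowance is made for infants without usable scans, because the protocol gives no figure for that.

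**What to change.** State one preterm number for WP2 in sections 3, 4.1 and 4.2, with the total and ratio that go with it, and give the same number in section 9.1. If the sponsor confirms 200, only the figure in section 4.2 changes, and 9.1 gains a sentence. If 300 was intended, sections 3 and 4.1 must change to 300 preterm and 400 dyads.

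Optionally, section 9.1 can add the precision that the chosen number delivers, with its assumptions labelled. For 200 and 100, for example: at two-sided alpha .05 and 90% power, with complete data, a term-preterm difference of 0.40 SD and a preterm-only correlation of about .23. For 300 and 100 the values are 0.37 SD and about .19.

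Keep the cortisol contrast as one of the three bases; labelling what its brackets are would help. Do not add a mediation power figure built on assumed path sizes.

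The cost is a wording amendment. If 200 is confirmed, recruitment does not exceed what sections 3 and 4.1 already plan.

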## 4.3 EXCLUSION CRITERIA

**WP1:** Neonatal death is the only exclusion criterion.

**WP2:** i) Preterm infants who are transferred to the study centre postnatally for intensive care; ii) Infants with congenital anomalies: structural or functional anomalies (e.g., metabolic disorders) that occur during intrauterine life and can be identified prenatally, at birth or later in life (WHO definition); iii) Infants with a contraindication to MRI at 3Tesla; iv) Preterm infants who are transferred to SCRH *ex utero* for intensive care are not included.

**WP3:** i) Children with congenital structural or functional anomalies (e.g., metabolic disorders) diagnosed after the neonatal period; ii) Children with acquired brain injury (e.g., traumatic brain injury, post meningitis); iii) Children with contraindication to MRI at 3Tesla.

## 4.4 CO-ENROLMENT

**WP1:** Not applicable.

**WP2:** The SCRH is an academic perinatal medicine centre that hosts observational research studies, and it is a recruiting centre for randomised controlled trials of therapies designed to improve the outcome of preterm infants and their mothers. Parents/carers of TEBC participants are encouraged to consider entry into such studies if eligible. Co-enrolment is informed by [POL008 Co-enrolment Policy](#), produced by the Academic and Clinical Central Office for Research and Development (ACCORD), which is a partnership between the University of Edinburgh and NHS Lothian Health Board. Co-enrolment will be recorded.

**WP3:** Co-enrolment for 5-year-old TEBC participants will be managed in line with the ACCORD Co-enrolment policy in WP2 in accordance with existing approvals from National Research Ethics Service (NRES) 16/SS/0154 and NHS Lothian Research and Development (2016/0255).

## 5 PARTICIPANT SELECTION AND ENROLMENT

### 5.1 IDENTIFYING PARTICIPANTS

**WP1:** Not applicable.

**WP2:** Women who present to the Simpson Centre for Reproductive Health with threatened preterm labour and for whom delivery is planned or expected at less than 32 weeks GA. The comparator group (non-exposed term infants) will be born to women who attend the Simpson Centre for Reproductive Health for antenatal care or delivery at >37 weeks GA. Potential participants will be identified using NHS systems: maternity TRAK and the neonatal electronic patient record. This will be restricted to clinically qualified members of the research team with honorary contracts for work in NHS Lothian Women's and Children's services, and members of the direct clinical care team. Both groups are trained in NHS Lothian's Information Governance procedures. The initial approach to potential participants will be by a member of the direct care team.

No person without existing permission to access NHS Lothian maternity electronic systems will be granted permission to identify participants. Only clinically qualified members of the research team who hold honorary contracts with NHS Lothian Women's and Children's services will identify potential participants. They will view NHS systems from within the NHS firewall within the RIE. They will not share the details of potential participants identified in the screening process with anyone other than the direct healthcare team. Clinically qualified members of the research team are not part of the direct care team.

**WP3:** Not applicable because participants already enrolled in a longitudinal study, TEBC.

### 5.2 CONSENTING PARTICIPANTS

**WP1:** Not applicable.

**WP2:** Consent to enter the study must be sought from each participant only after a full explanation has been given, an information leaflet offered and time allowed for consideration. Signed participant consent will be obtained in two stages for the preterm group: first, for data collection from antenatal period to the first week of postnatal life, and; second for data and samples over the rest of the neonatal period to the end of the study. Signed participant consent for all aspects of the study will be obtained in one stage for the comparator group. The right of the participant to refuse to participate without giving reasons will be respected, and will not affect the treatment they receive. All participants are free to withdraw at any time from the assessment protocol treatment without giving reasons and without prejudicing further treatment.

Consent to link to maternal routine samples before discard will be sought.

Consent to link participants with routinely collected data in health, social care and education, and consent to recontact for follow-on studies subject to additional funding will be sought.

Informed consent may only be taken by a member of the research team with training in GCP and procedures for research involving children and young people.

**WP3:** Consent procedures for data acquisition at 5-years have been approved by National Research Ethics Service (NRES) 16/SS/0154.

#### 5.2.1 Withdrawal of Study Participants

Participants are free to withdraw from the study at any point without necessarily providing reasons why they chose to withdraw, or a participant can be withdrawn by the Investigator. If withdrawal occurs, the primary reason for withdrawal will be documented in the participant's case report form if possible. To safeguard rights, the minimum personally-identifiable information possible will be collected.

## **6 STUDY ASSESSMENTS**

### **6.1 STUDY ASSESSMENTS**

**WP1:** Not applicable.

**WP2:** See Table 1.

**WP3:** See Table 2.

Table 1. WP2 assessments

Data collection point	Age	Data collection method	Sample type / domain	Test / task	Time implication for participants	Notes
1	Antenatal	administrative /electronic records & interview	Medical, deomgraphic, SES	Ethnic background and language spoken at home; parents' education and employment; family income; family structure, housing, neighbourhood quality, parents' mental health, social network and support  History and exposures: life events, prescribed medications, alcohol, smoking, substances, pregnancy complications	45 mins	
2	Birth	administrative /electronic records, questionnaire & tissue	Medical	Peripartum history and exposures, mother and infant Anthropometry	30 mins	
			Placenta	Structured histopathology rating and storage mRNA levels of glucocorticoid related genes	n/a	Collect and store
			Umbilical cord blood	i) 2ml umbilical cord blood; ii) dried blood spot for storage	n/a - sampling linked to clinical episodes	i) Endogenous glucocorticoids and metabolites (glucocorticoid release); glucocorticoid receptor in cord blood leukocytes (glucocorticoid signalling). ii) Inflammatory markers and DNA (collect and store)
			Hair, infant	Overall glucocorticoid secretion	15 mins	
			Hair, maternal	Overall glucocorticoid secretion	15 mins	
		Saliva	Methylome	10 mins	Term controls	
3	Neonatal	tissue	Dried blood spot	Inflammatory markers and DNA	n/a - sampling linked to clinical episodes	Collect and store
		tissue	Saliva	Methylome	10 mins	Preterms at term equivalent age
		tissue	Hair, infant	Overall glucocorticoid secretion	15 minutes	Preterms at term equivalent age
		biosample	Faeces	Microbiome	n/a	Collect and store: early (7-14 days) stool (cases and controls) and pre-discharge (cases)
		administrative /electronic records & direct observation	Medical	Anthropometry	n/a - linked to clinical episodes	
			Co-morbidities and exposures	Co-morbidities of preterm birth, medications, feed type and method; health status of control group.	n/a - sampling linked to clinical episodes	
			Parent IQ	National Adult Reading Test	15 mins	
		MRI	Brain structure and connectivity	sMRI, dMRI	90 minutes	Morphometric similarity networks, hierarchical complexity, magnetisation transfer imaging
		administrative /electronic records & questionnaire	Demographics & medical	Update perinatal history	15mins	
				Edinburgh post-natal depression scale	5 mins	
	Parenting daily hassles		10 mins			
	WHO-QOL		10 mins			
		Adult temperament questionnaire	10 mins			

Table 2. WP3 assessments

Age	Data collection method	Sample type / domain	Test / task	Time implication for participants	Notes
5 years	tissue: saliva	Epigenetics	Methylome	10mins	
		HPA axis	Cortisol	Timed: waking, 30 minutes after waking and before bed	
	direct observation	Anthropometry	Growth	5 mins	All
		Blood pressure	Hypertension	5 mins	All
		Ophthalmology	Refraction and acuity	20 mins	All
		Social cognition	Parent-child play; *Theory of Mind booklet task	30 mins	
		Executive function	Inhibition (Early Childhood Inhibition Touchscreen Task), Prohibition, and Spatial Working Memory	20 mins	All - direct assessment of EF
		Exploratory play	Novel toy task	5 mins	
		Reading	Woodcock-Johnson IV subscales	30 mins	All - direct assessment of reading
	IQ	Mullen Scales of Early Learning	40 mins	All - direct assessment of IQ	
	*MRI	Brain structure, connectivity, and function	sMRI, dMRI, fMRI	60 mins	
	eye-tracking	Social cognition	Face scanning	20 mins	Existing evidence that these distinguish between children born preterm and at term in infancy. Longitudinal profile by analysing with data from earlier timepoints
			Face pop-out		
		Social preferential looking			
	Processing / learning speed	Novel cue-target association (Posner task)			
	parent questionnaire	Medical and demographics	Diagnoses, health service utilisation	20 mins	
		Temperament / general	Strengths and Difficulties Questionnaire	5 mins	Capture sub-diagnostic traits and school readiness
		Language	Children's Communication Checklist	15 mins	Capture language including pragmatics and usage
		Autism	Social Communication Questionnaire: Current	5 mins	Capture social cognitive development
		ADHD	DUPaul ADHD rating scale	5 mins	Capture sub-diagnostic ADHD traits
		Executive function	Behaviour Rating Inventory for Executive Function (BRIEF)	15 mins	Parent-report measure of executive function
		Quality of life	WHO-QOL	10 mins	
		COVID impact	Centre for Developing Brain Questionnaire	15 mins	Parent report of pandemic impact on child and family
Feedback		Feedback form monitoring satisfaction with research project	5 mins	Evaluate acceptability of research setting, measures, info etc.	
teacher questionnaire	Visual perception	Cerebral Visual Impairment Inventory	20 mins		
	School milestones	CAIDS-Q	5 mins		
parent interview	Temperament / general	Strengths and Difficulties Questionnaire	5 mins	Capture sub-diagnostic traits and school readiness	
	Milestones	Record development against basic milestones, check diagnostic status	5 mins		
	General development	Vineland adaptive behaviour scales: parent rating forms	20 mins	Provide context for other measures	

## 6.2 LONG TERM FOLLOW UP ASSESSMENTS

**WP1:** Not applicable.

**WP2:** Study assessments end in the neonatal period (timepoint 3, see Table 1). Consent will be sought to re-contact for follow-on studies, subject to funding.

**WP3:** Participants are involved in a longitudinal study with separate arrangements for long term follow-up assessments.

## 6.3 STORAGE AND ANALYSIS OF SAMPLES

Three categories of imaging/biological samples will be collected:

**Neuroimaging** (neonatal and a five-year brain MRI). Neuroimaging data will be stored on a dedicated General-purpose computing on graphics processing units (GPGPU) server, accessible to members of the research team. Neuroimaging summary statistics will be stored in \*.CSV format and unprocessed neuroimaging data in standard NIFTI (\*.nii) format, organised according to the BIDS specification. Processing software will be shared using UoE Research Services Version control - GitLab platform.

**HPA axis activity** (umbilical cord blood and maternal and neonatal hair). Laboratory analyses of corticosteroids and their precursors and metabolites in plasma (2ml) and hair (>0.3cm 2cm from neonates, up to 3cm from mothers) and saliva (at 5 years on waking, 30 minutes after waking and bed-time) will be conducted at the University of Edinburgh Clinical Research Facility Mass Spectrometry Core. We have developed a robust method for steroid extraction from plasma (100µL) and tissues, with quantification of cortisol and related corticosteroids including cortisone, as well as dexamethasone and its metabolites, simultaneously by liquid chromatography tandem mass spectrometry (LC-MS/MS), using a Sciex QTRAP® 6500 (Warrington, UK) operated in positive ion electrospray ionisation with a Waters Acquity™ UPLC system (Manchester, UK). We will include recently characterised DNAm signatures of HPA axis-immune activity such as FKBP5 (FK506-binding protein 51). Umbilical cord blood and placental tissue (WP2) will be stored in the Edinburgh Reproductive Tissue Biobank (ERTBB) prior to analysis in Edinburgh Clinical Research Facility Mass Spectrometry Core. Any residual material will be returned to ERTBB for storage and future use subjects to new ethical approval. Maternal and infant hair will be stored in MRC CRH at room temperature before transfer to University of Edinburgh Clinical Research Facility Mass Spectrometry Core ([name] is shared custodian with [name] (Co-Investigator)).

**DNA methylation profile** (saliva). DNA from saliva will be extracted using prepIT.L2P reagent (DNA Genotek, Ontario, Canada). DNA will be bisulfite converted and methylation measured using Illumina HumanMethylationEPIC BeadChip (Illumina, San Diego, CA, USA) at the Edinburgh Clinical Research Facility Genetics Core (ECRF), Edinburgh, UK; the epigenetic measure of chronic inflammation will be calculated for each participant. Transcriptions will be .CSV format. Raw data is .IDAT file format. All formats and software platforms support sharing and long-term validity. Remaining DNA will be stored at ECRF for possible future analysis subject to new ethical approvals.

**Dried blood spots** (umbilical cord blood). Blood spots will be collected using Schleicher and Schuell 903 filterpaper (6 x 3.2mm spots per subject). Cards will be stored at -20°C in the MRC CRH and analysed in batch, subject to funding.

**Placenta.** Samples will be stored at -80°C in the Edinburgh Reproductive Tissue BioBank (ERTBB); [name] is shared custodian with [name] (Co-Investigator).

**Gut microbiota** (neonatal faeces). The gut microbiome plays a role in human health and disease including child development, and it is modified by age at birth, sex, mode of delivery, antibiotic exposure, and feed type. The microbiome may mediate interactions of the gut-brain axis. Faecal samples will be collected at two time points: early stool, 7 to 14 days after birth (all infants in WP2) and

stool pre-discharge from hospital (for preterm group). Samples will be processed and stored at  $-80^{\circ}\text{C}$  in the MRC CRH for later analyses, subject to funding.

Our intention is that the data derived by this programme will be available for use by the research and policy communities in perpetuity. **(i) Neuroimaging**; raw neuroimaging data acquired in Edinburgh are archived indefinitely. The image processing server is linked by automatic daily back-up to the off-site Edinburgh Compute and Data Facility (ECDF). The compute component of ECDF, Eddie, has built-in redundancy with error check and 'self-healing,' and is itself backed-up using 2 tape systems. **(ii) HPA axis**; data will be stored securely under password protection using UoE DataShare, which is backed-up and maintained through UoE IT systems. **(iii) DNAm**; Raw .IDAT files will be stored on GEO indefinitely.

We have costed for University of Edinburgh storage with guaranteed backup and resilience for all new data generated. In the long-term, the University of Edinburgh provides a DataVault data retention service to archive golden copy research data (<https://www.ed.ac.uk/information-services/research-support/research-data-service/after/datavault>), which is also appropriate for sensitive data types; no charges apply to  $\leq 100\text{GB}$ , which the phenotypic dataset will not exceed. A golden/master copy of new data will be migrated onto this service as part of the process of data curation at the end of the project.

HPA axis and DNAm data will be stored on UoE Research Data Management servers, supported by Information Services. The data in the RDM file-store is automatically replicated to an off-site disaster facility and is backed up with a 60-day retention period, with 10 days of file history online.

